### **7.2.3            Withdrawal of Patients**

Patients will be informed that they have the right to withdraw from the study at any time, without prejudice to their medical care, and that they are not obliged to state their reasons.

Any withdrawal, and reasons for withdrawal, must be fully documented in the electronic case report form (eCRF) and source documents and the patient followed by the investigator/investigative staff. Even after the study is completed at the Follow-Up visit, the investigator/investigative staff will, regardless of reason for withdrawal, record any patient data they receive concerning serious adverse events (SAEs), and all drug-related non-serious AEs, and report these in the eCRF. Withdrawn patients will not be replaced.

Patients will be withdrawn in the following circumstances:

- A patient's desire for withdrawal for any reason
- Lost to follow-up (every effort must be made to contact the patient; a certified letter must be sent)
- An AE that, in the opinion of the Investigator, necessitates withdrawal
- Death
- A patient's substantial noncompliance (study drug compliance) or protocol violation
- An Investigator's opinion that continuing the patient in the study is not appropriate. The Investigator may withdraw a patient at any time if it is considered to be in the patient's best interest

A patient who withdraws from treatment prematurely will have EOT (Visit 6) assessments at the time of withdrawal and a Follow-Up assessment (Visit 7) approximately 2 weeks following the last dose of study drug, and the patient will be recorded as withdrawn.

#### **7.2.4        Study Termination by Sponsor**

This study may be terminated at any time by the Sponsor if serious side effects should occur, if the Investigator does not adhere to the protocol, or if, in the Sponsor's judgment, there are no further benefits to be achieved from the study. In this event, the Sponsor or its designee will inform the study investigators, institutions, and all regulatory authorities.

The Sponsor may temporarily or permanently discontinue the study at an investigative site at any time for safety, ethical, compliance, or other reasons. If this is necessary, the Sponsor will endeavor to provide advance notification to the site. If a site or the study is

---

suspended or discontinued, the Investigator/investigative staff will be responsible for promptly informing the IRB. If required by local regulations, the Sponsor or its designee will be responsible for informing the IRB and the regulatory authority of study or site discontinuation. In such an event, all study data and unused study drug must be returned to the Sponsor or its designee.

## **8. TREATMENT OF PATIENTS**

### **8.1 Identity of Study Drug**

Elobixibat and placebo will be supplied as tablets for oral administration during the Treatment phase of the study. White tablets containing elobixibat or placebo will be provided.

The elobixibat and placebo tablets will be identical in appearance. Tablet filling weight will also be identical for elobixibat and placebo. Bottles containing 34 tablets will be given to the patient at each visit. Refer to the study reference manual.

### **8.2 Administration of Study Drug**

Patients will be dosed with elobixibat at a dose of 5 mg or placebo once daily for 16 weeks. Study drug will be dispensed to the patient at Visits 2-5 together with instructions on how to store and take the drug. Study drug compliance will be evaluated at each study visit.

Elobixibat should be taken in the morning, prior to the first meal. On clinic visit days when laboratory assessments are conducted, study drug should be taken after the visit and after laboratory samples are taken.

### **8.3 Study Treatment Packaging and Labeling**

#### **8.3.1 Packaging and Labeling**

The tablets will be packed in high-density polyethylene bottles, with child-proof polypropylene caps. Packaging and labeling will be prepared to comply with applicable regulatory requirements.

#### **8.3.2 Storage**

Treatment bottles containing elobixibat tablets should be stored and dispensed in accordance with regulations in their original containers. The storage facility at the investigative site should be locked and the storage temperature should be between 15°C and 25°C.

Caregivers should be informed of appropriate storage conditions (i.e., room temperature, between 15°C and 25°C).

Any deviations from the recommended storage conditions should be immediately reported to the Sponsor and the study drug should not be used until authorization has been given by the Sponsor.

### **8.3.3 Blinding and Randomization of Study Drug**

A double-blind design is employed so that both the investigators and the patients will be unaware of the treatment assignment during the study.

After written informed consent is obtained from an eligible patient, a 6-digit patient number will be assigned. The first 3 digits will be the site number followed by a 3-digit patient sequence number. This number will be created and allocated by the site when the patient first enters at Screening. The randomization codes will be computer-generated by a statistician independent from the project team. The randomization will be done in blocks to ensure approximate balance between dose schemes (1:1). Randomization codes will be assigned sequentially as patients become eligible for randomization.

Patients who are eligible for randomization will be assigned a unique 4-digit randomization number by the Interactive Web Response System (IWRS). This randomization number identifies which treatment will be allocated to the patient. Patients who withdraw from the study after randomization visit are not to be replaced and their randomization number will not be reused.

To ensure blinding, the study drug and the matching placebo have the same shape and size. Labels on the treatment bottles will not identify the treatment to which a patient has been randomized. Traceability of the treatment is ensured by the bottle number.

The 5-digit bottle number will identify the study-drug bottle and will be detailed on the study-drug label. Dispensing of the study drug will be coordinated by IWRS.

The system will assign a study-drug number corresponding to the randomization arm. The randomization number will be used in the background only to ensure that there is no unblinding and will not be displayed to end-users in the IWRS.

### **8.4 Procedure for Breaking the Randomization Code**

Should a situation arise where unblinding is urgently required, i.e., only where knowledge of the study drug is required to adequately manage a life-threatening situation,

the Investigator at that study site may perform immediate unblinding through IWRS. The responsibility to break the treatment code in emergency situations resides solely with the Investigator. The Investigator should make every effort to discuss the rationale (status and outcome) for emergency unblinding with the Sponsor's Medical Monitor as soon as possible to review the individual patient details.

The study-site Investigator and appropriate project team members will be authorized to access the emergency unblinding functionality within the IWRS. Once the randomization code is broken for a patient, he/she must be withdrawn from the study and all assessments and procedures for Visit 6/EOT should be performed. Once a randomization code has been broken, the Investigator must inform the project team and Sponsor's Medical Monitor in writing within 24 hours. In case of technical issues accessing the system online, please see the IWRS site user manual for contact telephone numbers for the help desk 24/7 system support.

## **8.5 Patient Compliance**

Patients will return all unused study drug at Visits 3 through 6. The study-site staff will count all returned drug, assess compliance, and record details in the eCRF.

Any noncompliance will be documented and explained in the source documents.

Treatment compliance =  $100 \times ([\text{number of study drug dispensed} - \text{number of study drug returned}] / \text{number of study drug that should be taken})$

Treatment compliance between 80% and 120% is acceptable.

## **8.6 Study Drug Accountability**

Records shall be maintained of the delivery of study treatment(s) to the study site(s), of the inventory at the study site(s), of each use of the study treatment(s) for each patient and the return or destruction of used and unused study treatment(s). Local destruction of used/unused study treatment(s) will follow institution standard operating procedures (SOPs) and will require Sponsor pre-approval.

These records shall include dates, quantities, batch numbers, expiry dates, and the unique code numbers assigned to the study drug and to the study patients.

The Investigator will be responsible for ensuring that the records adequately document that the patients were provided the quantities specified in the protocol and that all study drug received from the Sponsor or its designee is reconciled.

### **8.7 Concomitant Therapy and Prohibited Medications**

The Investigator will note all ongoing medication and any medication recently stopped (within 3 months prior to Visit 2) in the eCRF. At Visits 2 through 6, all changes in medication (stopping or starting new medication or changes in dose) will be recorded in the eCRF.

All medications taken by a patient within 3 months prior to the first intake of study drug are regarded as prior medication.

All medications taken by a patient on or after the first intake of study drug, and which continue to be taken during the study, are regarded as concomitant medication.

## **9. ASSESSMENT OF EFFICACY**

### **9.1 Efficacy Endpoints**

#### **9.1.1 Primary Efficacy Endpoint**

The primary efficacy endpoint is the change from Baseline in serum LDL-C at Week 16.

#### **9.1.2 Secondary Efficacy Endpoints**

Secondary efficacy endpoints include the following:

- Absolute change from Baseline to Week 16 in liver fat fraction (%) as measured by MRI-PDFF
- Absolute change from Baseline to Week 16 in total liver fat (mL) as measured by MRI
- Change from Baseline to Week 16, and Follow-Up in the following:
  - Serum ALT, AST, and gamma-glutamyl transferase
  - HDL-C, non-HDL-C, LDL-C/HDL-C ratio, and triglycerides
  - Total bile acids

#### **9.1.3 Exploratory Efficacy Endpoints**

The following exploratory efficacy endpoints will be assessed:

- Change from Baseline (unless otherwise specified) to Week 4, Week 8, Week 12, Week 16, and Follow-Up in the following:
  - Fasting glucose, insulin, homeostatic model assessment-insulin resistance, HbA1c, free fatty acids
  - GLP-1, FGF-19, and C4 levels
  - High-sensitivity CRP
  - Lanosterol and beta-sitosterol
  - Body weight, BMI, waist circumference, and waist-to-hip ratio

- Apolipoprotein A1 and Apolipoprotein B

## **9.2 Efficacy Assessments**

### **9.2.1 Lipid Profile**

Fasting blood samples for analysis of LDL-C will be drawn at all visits, according to the schedule of assessments (Table 1). Fasting should be for at least 8 hours prior to the collection of the blood sample. Samples will be processed and transported to a central laboratory per instructions in the study reference manual.

### **9.2.2 Magnetic Resonance Imaging**

Patients will have an MRI at Screening and EOT to assess liver fat by MRI-PDFF, and total liver volume. Details of the image acquisition and analysis can be found in the study reference manual.

### **9.2.3 Total Bile Acids**

Fasting blood samples for analysis of total BA will be drawn at all visits, according to the schedule of assessments (Table 1). Fasting should be for at least 8 hours prior to the collection of the blood sample. All BA results during the treatment period will be blinded. Samples will be processed and transported to a central laboratory per instructions in the study reference manual.

### **9.2.4 Biomarkers and Blood Samples for Future Testing**

Blood samples for analysis of additional markers of disease, fibrosis, inflammation, and cardiovascular risk factors, and other pharmacodynamic markers will be drawn at the appropriate visits, according to the schedule of assessments (Table 1). These include a bile acid profile, including primary and secondary bile acids, interleukin-6, Pro-C3, tumor necrosis factor alpha, and cytokeratine-18. Samples will be processed and transported to a central laboratory per instructions in the study reference manual.

## **10. ASSESSMENT OF SAFETY**

The timing and frequency of safety assessments are described in Section [7.1.3](#) and in [Table 1](#).

The primary safety analysis will include the occurrence of treatment emergent adverse events (TEAE) and TEAEs categorized by causality, severity, and seriousness assessments made by the Investigator by comparing study drug exposure to placebo.

Trends in safety will also be evaluated for the following assessments:

- AEs, including discontinuations due to AEs
- Physical examinations
- Concomitant medications
- Vital signs
- 12-lead ECG
- Laboratory test results (including clinical chemistry, hematology/coagulation, and urinalysis)

### **10.1 Adverse Events**

#### **10.1.1 Definitions and Investigator Assessments**

An AE is defined as any untoward medical occurrence in an enrolled patient regardless of causal relationship with study drug. An AE can therefore be any clinically significant unfavorable and unintended sign, symptom, or disease that occurs once a patient is enrolled (ICF is signed) in the study until the patient is discharged from the study, whether or not related to the study drug.

#### **10.1.1.1 Clinical Significance**

Clinical significance is defined as any abnormal finding that results in further clinical investigation(s), treatment(s), or the diagnosis of a new condition. Patient reported events and protocol mandated laboratory values, vital signs, and physical examination findings can be considered clinically significant (i.e., an AE) if there is a deterioration as compared to Baseline. Examples of clinically significant worsening from Baseline could

include, but is not limited to, events causing withdrawal from the study and events requiring medical intervention outside of the study causing apparent clinical manifestations or judged to be relevant by the Investigator.

#### 10.1.1.2        Serious Adverse Events

Serious criteria are applied by the investigator to each AE as specifically defined below. These criteria are used to determine whether an AE is serious or non-serious. The assessment is made independently of severity assessment (Section 10.1.1.3). For example, the development of a severe rash that occurs after signing of the ICF may not meet serious criteria as defined below and therefore would be considered a severe, non-serious AE.

Any AE that meets any 1 of the following 6 criteria is considered to be an SAE:

- The outcome of the AE is **death**
- The AE is immediately **life-threatening**. Life-threatening means that the patient is, in the opinion of the Investigator, at immediate risk of death from the reaction as it occurred. This does not include an AE that, if more severe, might have caused death
- The AE results in persistent or significant **disability/incapacity**. Disability means a substantial disruption of a person's ability to conduct normal life functions
- The AE requires or prolongs **hospitalization**
- The AE results in a **congenital anomaly/birth defect**
- **The AE is an important medical event.** Important medical events may meet serious criteria should the Investigator assess that they may significantly jeopardize the patient, represent a significant hazard, or require medical/surgical intervention to prevent one of the outcomes listed above. Examples of potential SAEs based on these criteria include, but are not limited to, allergic bronchospasm requiring intensive treatment in an emergency room or at home, blood dyscrasias or convulsions even if they do not result in inpatient hospitalization, or the development of drug dependency and drug abuse.

**10.1.1.3 Adverse Events of Special Interest**

An adverse event of special interest (AESI) should be recorded as an AE in the eCRF as outlined in Section 10.1.2 and reported using the SAE/AESI Report Form outlined in Section 10.1.3.

For this study, any occurrence of ischemic colitis should be reported as an AESI.

**10.1.1.4 Severity Assessment**

Severity assessments are based on the intensity of the event in relation to expectation. The Investigator will assess the intensity of AEs based on the following definitions:

- Mild (awareness of sign or symptom, but easily tolerated)
- Moderate (discomfort sufficient to cause interference with normal activities)
- Severe (incapacitating, with inability to perform normal activities)

Severity is a measure of intensity where seriousness is defined by the criteria outlined in Section 10.1.1.2. An AE of severe intensity need not necessarily be considered serious. For example, nausea that persists for several hours may be considered severe nausea, but not meet serious criteria, and therefore would be assessed as a severe AE but not an SAE.

**10.1.1.5 Causality Assessment**

The Investigator determines the causality of all AEs to the study drug using medical judgment and considering all relevant factors such as (but not limited to) the underlying study indication, coexisting disease, concomitant medication, relevant history, pattern of the AE, temporal relationship to the study drug, and de-challenge or re-challenge. The causality assessment of the AE/SAE is to be made as follows:

**Related to Study Drug (Possibly, Probably, or Definitely Related)**

Based on medical judgment, there is at least a reasonable possibility that the study drug caused the event; one or more of the following criteria apply:

- The event follows a reasonable temporal sequence from administration of study drug

- The event could not be reasonably attributed to the known characteristics of the patient's clinical state, environmental or toxic factors, or other modes of therapy administered to the patient
- The event follows a known pattern of response to study drug
- The event disappears or decreases on cessation or reduction in dose of the study drug. (It should be noted that in some situations an AE will not disappear or decrease in intensity upon discontinuation of study drug despite other clear indications of relatedness)
- The event reappears or worsens when the study drug is re-administered

### **Unrelated to Study Drug (Unlikely or Unrelated)**

Based on medical judgment there is no reasonable possibility that the study drug caused the event; one or more of the following criteria apply:

- The event does not follow a reasonable temporal sequence from administration of study drug
- The event could be reasonably attributed to the known characteristics of the patient's clinical state, concurrent illness, environment or toxic factors, or other modes of therapy administered to the patient
- The event does not follow a known pattern of response to study drug
- The event does not disappear or decrease on cessation or reduction in dose of the study drug, and it does not reappear or worsen when the study drug is re-administered

#### **10.1.2 Recording of Adverse Events**

It is the Investigator's responsibility to assess whether each untoward event is a clinically significant worsening from Baseline, thereby considered an AE. For all AEs, the severity, seriousness, and causality to study drug for each AE as outlined in Section 10.1.1 will be assessed and recorded in the eCRF.

All serious and non-serious AEs are collected once the patient has signed the ICF and until the post-treatment follow-up (Visit 7) or 14 days after the last dose of study drug.

Any AEs or SAEs that are unresolved at the patient's last AE assessment are followed up by the Investigator until resolution or stabilization up to the database lock and recorded in the eCRF. The Sponsor retains the right to request additional information for any patient with ongoing AE(s) or SAE(s) at the end of the study.

TEAEs are defined as any AE that occurs after first dose of study drug. All AEs that occur in the Screening period, i.e., after enrollment and prior to randomization, will be collected on the eCRF as non-TEAEs.

If there is a clinically significant deterioration of a laboratory value/vital sign or other routine study assessment that is associated with a diagnosis, the clinical diagnosis will be reported as an AE and the associated signs and symptoms will be considered additional information unless the sign or symptom is more severe than expected given the diagnosis. For example, if an Investigator diagnoses a study patient with hepatitis during the study period, hepatitis would be considered the AE and the concomitant signs and symptoms of abdominal pain, vomiting, and elevated ALT and AST would not be reported separately unless, in the opinion of the Investigator, one of these signs or symptoms is more severe than expected and therefore a separate AE assessment is indicated.

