#### 5.4 Risk/Benefit

Elobixibat is orally administered and acts locally in the gut where it binds reversibly to the IBAT to decrease the reuptake of bile acids into the liver, thereby increasing the concentration of bile acids in the colon. Due to its mechanism of action, most adverse events (AEs) are gastrointestinal (GI) tract disorders, such as abdominal pain, diarrhea, abdominal distention, flatulence, and nausea; the incidence of these has increased with increasing dose levels. Diarrhea has been the most prominent dose-limiting side effect. No clinically significant findings in laboratory measures or electrocardiograms (ECGs) have been reported. Based on postmarketing case reporting, ischemic colitis will be monitored as an adverse event of special interest for elobixibat.

There is no established benefit for subjects participating in this Phase 2 study. Based upon these data, the risk/benefit for subjects participating in this trial is acceptable.

This study will be conducted in compliance with the protocol and with the International Council on Harmonisation (ICH) guidelines on GCP.

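### The protocol's definitions and its recording rule conflict on what counts as an AE, so mild untreated GI symptoms, the drug's main named risk, may be recorded but need not be.

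*Protocol*

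**What the plan says.** All references are to Protocol version 3.0 unless stated.

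- **Section 10.1.1** opens: "An AE is defined as any untoward medical occurrence in an enrolled patient regardless of causal relationship with study drug". The next sentence narrows this: "An AE can therefore be any clinically significant unfavorable and unintended sign, symptom, or disease that occurs once a patient is enrolled".
- **Section 10.1.1.1** opens: "Clinical significance is defined as any abnormal finding that results in further clinical investigation(s), treatment(s), or the diagnosis of a new condition". It then says that patient-reported events, as well as laboratory, vital-sign and examination findings, "can be considered clinically significant (i.e., an AE) if there is a deterioration as compared to Baseline". Its list of examples is expressly not exhaustive and ends with events "causing apparent clinical manifestations or judged to be relevant by the Investigator".
- **Section 10.1.2**, the recording instruction, gives the Investigator the "responsibility to assess whether each untoward event is a clinically significant worsening from Baseline, thereby considered an AE". It also says that serious and non-serious AEs are all collected.
- **Section 10.1.1.4** has a lowest severity grade of "Mild (awareness of sign or symptom, but easily tolerated".
- **Section 5.4** says most AEs of this drug are GI disorders that become more frequent with dose, and adds: "Diarrhea has been the most prominent dose-limiting side effect".

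Safety and tolerability is a secondary objective (Section 6.2). The primary safety analysis is the occurrence of TEAEs by causality, severity and seriousness, compared with placebo (Section 10).

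**The concern.** The opening definition takes in every untoward event, while the recording rule takes in only those judged a clinically significant worsening. A mild GI symptom that nobody treats or investigates is the sort of event on which the two can give different answers, and this drug is expected to cause such symptoms.

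If sites apply the narrower wording, those symptoms never reach the TEAE tables, the severity tables or the comparison with placebo. If some sites apply it and others do not, the counts partly reflect site habit. With about 46 patients at up to 15 sites, the average is about 46 / 15 = 3 patients per site if all open and recruit evenly, so a few sites' habits could move the totals.

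**Working it through.** **One case through each rule.** Take a patient who reports loose stools that are new since Baseline, easily tolerated, not treated and not investigated.

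| Text | Must this event be recorded? |
|---|---|
| 10.1.1, first sentence | Yes. It is an untoward occurrence. |
| 10.1.1, second sentence | Unclear. It names clinically significant symptoms and is silent on the rest. |
| 10.1.1.1, first sentence | No. There was no investigation, treatment or new diagnosis. |
| 10.1.1.1, second sentence | It may be. The event is worse than Baseline, but the verb is permissive. |
| 10.1.1.1, examples | It may be, if the Investigator finds it relevant. The grammar leaves open whether relevance stands alone or only qualifies events that need medical intervention. |
| 10.1.2 | The Investigator decides, using the 10.1.1.1 test. |
| 10.1.1.4, Mild | The event fits the grade, but grading comes after AE status is settled. |

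The event may therefore be recorded or left out, and either choice has textual support. The statement in 10.1.2 that all non-serious AEs are collected does not settle it, because it applies only to events already classed as AEs.

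**Whether anything else captures the event.** The only AESI is ischemic colitis (Section 10.1.1.3). Table 1 has AE review at every visit but no GI diary or symptom scale. SAP Section 3.4 tabulates recorded TEAEs, including a mild category, and adds no rule on what is recorded.

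**Size.** The documents state no figure to reproduce. The illustration below assumes its rates: true GI incidence of 40% on active and 15% on placebo, with 30% to 60% of patients with a GI event having only mild, no-action symptoms. Let f be the fraction of affected patients who go unrecorded. It runs from 0 (every mild event entered) to 0.6 (mild share 60%, none entered). Recorded incidence = true incidence × (1 − f), with the same f in both arms.

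| f | Active | Placebo | Difference | Ratio |
|---|---|---|---|---|
| 0 | 0.40 | 0.15 | 0.25 | 2.67 |
| 0.3 | 0.40 × 0.7 = 0.28 | 0.15 × 0.7 = 0.105 | 0.175 | 2.67 |
| 0.6 | 0.40 × 0.4 = 0.16 | 0.15 × 0.4 = 0.06 | 0.10 | 2.67 |

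With 23 per arm, the largest loss is 23 × 0.40 × 0.6 = 5.5 patients on active and 23 × 0.15 × 0.6 = 2.1 on placebo.

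The direction depends on equal f. A loss of 0.6 on active only would leave 0.16 − 0.15 = 0.01. A loss of 0.6 on placebo only would give 0.40 − 0.06 = 0.34, an overstatement.

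**The case against.** A reader might infer that an event becomes an AE only if it leads to investigation, treatment or a new diagnosis, so that untreated mild diarrhea is shut out. The documents do not support that. It rests on the first sentence of Section 10.1.1.1 alone. The second sentence lets a patient-reported deterioration count with no work-up or treatment, and the examples are open-ended. Exclusion criterion 18 keeps out patients with a history of conditions associated with diarrhea, so new loose stools would ordinarily be a change from Baseline. The opening definition and the Mild grade also point toward recording, since that grade would have little use if untreated mild symptoms were never AEs. This answers the strict reading. It does not answer the discretion that remains, because none of these texts makes recording obligatory.

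A second tempting inference is that the drug will be made to look better tolerated by a known margin. That is not supported either. Investigators judge blinded (Section 8.3.3), the documents show no mechanism for unequal recording, and proportional loss leaves the ratio intact. The absolute rates and their difference still shrink.

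A third is that the AE page is the only record of GI symptoms. The schedule lists no other, but the eCRF and study reference manual are not available here, and they may tell sites how to ask about and enter symptoms.

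It is also fair to say that safety is summarized descriptively (SAP Section 3.4), in an exploratory study, and that the primary endpoint is untouched. That limits the consequence. Tolerability is still a stated objective, and descriptive counts are its whole evidence.

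**Conclusion.** The inconsistency is real. Sections 10.1.1, 10.1.1.1 and 10.1.2 conflict, and neither the AESI rule nor the SAP resolves the conflict. As written, recording of mild untreated GI symptoms is left to Investigator discretion, so sites may differ and absolute TEAE incidences may be understated.

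The active-minus-placebo difference is understated as long as more events are lost from the active arm than from placebo. That follows if the drug causes more of them and the loss is proportional. The amount cannot be derived. On the assumed rates above with equal loss, a true 25-point difference would be recorded as anything from 10 to 25 points, with the ratio unchanged. No single figure in that range is better supported than another. The conclusion about the text needs none of these assumptions.

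The recording rule reads the same in versions 1.0 and 2.0, so the version 3.0 amendment did not introduce it.

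**What to change.** Reconcile the three sections:

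1. **10.1.2:** state that every sign or symptom that is new or worse than Baseline is recorded as an AE, whether or not it needs investigation or treatment.
2. **10.1.1.1:** confine the clinical-significance test to laboratory, vital-sign, ECG and physical-examination findings.
3. **10.1.1:** remove the clinical-significance qualifier from the second sentence, so that it agrees with the first.

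This takes a wording change and a reminder to sites. No visit, procedure or planned table changes. The downside is that more mild AEs will be entered and the reported TEAE rate will rise in both arms.

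New wording cannot recover events already left out. The SAP speaks of treatment received and of visits already missed (Sections 2.2 and 4), so at least some patients had been treated by then. For them, query sites where that is still possible, and state the possible under-recording of mild events as a limitation wherever tolerability is reported.
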